6.2 Outcomes

The *primary outcome* will be whether physicians intensified treatment at the visit targeted by the intervention. Intensification of treatment will include an increase in dose of an existing antihypertensive medication, adding an additional medication, or rotation of one medication to another that is stronger or more appropriate for the patient (e.g. changing hydrochlorothiazide to furosemide for a patient with chronic kidney disease). These will be measured using prescribing information from the EHR on the day of the patient's visit.

The *secondary outcome* will be the change in systolic blood pressure over 6-months of follow-up in each intervention arm compared to control. The initial value will be the systolic blood pressure at the time of enrollment that determined the patient's eligibility for participation. The follow-up blood pressure will be the last blood pressure available in the EHR within 6 months after the visit targeted by the intervention. Based on prior studies in a similar local healthcare system, we anticipate approximately 20% missingness rate for the follow-up blood pressure within 6 months, and that this will likely be non-differential between treatment arms.²⁵ Should there be sufficient missing data (e.g., >10%), we will use multiple imputation to handle this. In specific, we will use 20 imputations with Proc MI in SAS to impute any estimated values using fully conditional specification. Analyses will then be conducted on each imputed dataset and combined using Rubin's rules.²⁶ We will perform a complete case analysis as a sensitivity analysis.

Each post-intervention interview will be moderated by trained study staff using a semi-structured interview guide that asks physicians about barriers to hypertension treatment intensification, perspectives on different intervention arms, and suggestions for improvement.

We will use results from the physician interviews and study staff expertise to select variables for inclusion in the predictive modeling analysis. These variables will all be available in either the EHR or baseline physician surveys and will include, but are not limited to: physician age, gender,

practice setting, baseline trends in hypertension prescribing, practice location, and patient case-mix. We will also collect patient data that include but are not limited to: sociodemographic data, medical history and comorbidities, baseline resource utilization in prior 12 months (i.e., number of visits), and biometric values (e.g., serum creatinine, systolic/diastolic blood pressures).

6.3 Adverse events and unanticipated problems

Oversight:

Oversight of the pilot will be the responsibility of Drs. [name] and [name], the Principal Investigators.

The PIs and study team will meet on a regular basis throughout the study period and will be in direct contact with clinical leadership involved in the project to obtain ongoing feedback.

De-identified study data will be accessible at all times for the MGH PI and coinvestigators to review, if applicable. We will also ensure that all protocol deviations for the pilot study are reported to the NIH and the IRB according to the applicable regulatory requirements. Compliance of regulatory documents and study data accuracy and completeness will be maintained through an internal study team quality assurance process.

Definition:

Adverse Event (AE): Any untoward or unfavorable medical occurrence in a human study participant, including any abnormal sign (e.g. abnormal physical exam or laboratory finding), symptom, or disease, temporally associated with the participants' involvement in the research, whether or not considered related to participation in the research.

- Adverse Events will be classified using the following rating scales:
 - Severity: Mild, Moderate or Severe
 - Mild: Awareness of signs or symptoms but are easily tolerated
 - Moderate: Events introduce a low level of inconvenience or concern but may interfere with daily activities but are usually improved by simple therapeutic measures.
 - Severe: Events interrupt the participants' normal daily activities and generally require systemic drug therapy
 - Expectedness: Unexpected or Expected

- Unexpected: nature or severity of the event is not consistent with the condition under study
- Expected: event is known to be associated with the intervention or condition under study.

Serious Adverse Event (SAE): Any adverse event that:

- results in death
- is life threatening, or places the participant at immediate risk of death from the event as it occurred
- requires or prolongs hospitalization
- causes persistent or significant disability or incapacity
- results in congenital anomalies or birth defects
- is another condition which investigators judge to represent significant hazards.

Determination:

Given the minimal risk nature of the study which aims to increase guideline concordant care for patients with persistently elevated blood pressures, we do not anticipate any SAEs or AEs.

Patients' own primary care physicians will have ultimate decision-making authority for prescribing choices, as they would in routine clinical practice, and we expect any adverse events related to hypertension medication intensification, such as hypotension or bradycardia, to be the same or less as those experienced in routine clinical care, given the focus on patients with clinical inertia. In the SPRINT¹⁴ trial, which tested intensive BP control among patients age 75 or older, similar rates of serious adverse events occurred in the intensive-treatment group and in the standard-treatment group. In this study, we are using standard blood pressure targets and include a younger patient sample who have persistently elevated blood pressure.

Reporting:

As previously described, any adverse events as part of this study are expected to be similar, or lower, than those anticipated in routine hypertension care. The study team will not be providing any direct care to patients and all treatment decisions will ultimately be made by the patients' medical teams at Massachusetts General Hospital. Any adverse event will be handled in the course of regular clinical care. Because we are not directly intervening upon patients and will have no patient contact during this study, prospectively tracking adverse events is infeasible. However, physicians will have contact information for our research team to report any concerns, and we will be in

regular contact with practice and DGIM leadership to monitor for any adverse events that come to attention through any of those channels. Therefore, while we will not be actively monitoring the occurrence of adverse events, which if done would require patient contact and detailed patient-level chart-reviews, we anticipate that the study team will be informed of any AEs or SAEs that do occur. [name] Director of Population Health and Quality for MGH DGIM and the Associate Medical Director of the Massachusetts General Physician Organization is engaged in support of this project and will help with monitoring of physician feedback that gets routed through traditional departmental channels.

If we become aware of any AEs or SAEs throughout the course of the study, we will collect this information. Any reports of deaths will be submitted to the NIA Program Officer and to the Safety Officer (SO) within 24 hours. Any unexpected SAEs will be reported to the NIA PO, SO and the IRB within 48 hours of the study's knowledge of the SAE. All other reported SAEs and AEs received by the study team will be reported to the NIA Program Officer and to the SO quarterly, unless otherwise requested by the Safety Officer or Roybal Center Program Data Safety Monitoring Board (DSMB).

7. Statistical Considerations

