3.7 Data sources

Sources of research material, data that will be recorded, when data will be collected

Data regarding patients' medical history, disease control, medication use and health care utilization will be obtained from EHR data, supported by Epic Systems, Inc. The data warehouses for this organization reside in an Oracle 9i environment and consists of the Clarity and Payer databases. The Clarity database is a relational database that contains clinical and financial information from the Epic Suite of products; including the electronic medical record system (EpicCare), the appointment scheduling system (Cadence), the patient accounting

system (Resolute), the patient web portal and the master patient index (Identity). The various tables within the Clarity database are refreshed on a daily, weekly or monthly basis.

Linkages to subjects, access to subject identities

Individually-identifiable data are maintained for patient care purposes within the MGB network and are needed to identify patients for evaluation and to monitor care recommendations by physicians. Without this linkage, we could not fulfill the study's objectives. To protect the confidentiality of these data, only the minimal necessary research staff will have access to personal identifiers. This will be necessary for linking data and contacting physicians. After linkage is completed and study variables are created, all identifiable information will be deleted from the study database. All research staff are properly trained in research management and will be approved by the IRB. All personally identifiable health information will be kept under lock and key.

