8.4 Safety oversight

General oversight of these particular projects by the PIs ([name] and [name]) will occur throughout the study period, including regular contact with clinical primary care leadership to obtain ongoing feedback. In addition, this protocol will undergo Institutional Review Board (IRB) evaluation. Our trial has been registered with clinicaltrials.gov.

We will have oversight from both the NIA Director-approved Roybal Centers Program Data Safety Monitoring Board (DSMB) and a Program Officer-approved independent Safety Officer (SO) for all aspects of this research. The DSMB will act in an advisory capacity to the NIA to monitor participant safety, evaluate the progress of the study, and review procedures and management of the study. The SO will provide the Program DSMB with periodic safety reports. Our plan for data and safety monitoring also includes oversight by the project principal investigators (Drs. [name] and [name]) throughout the study period.

Meetings of the DSMB will be held regularly (e.g., every six to nine months) at the call of NIA or the DSMB Chair and review data related to study protocols and ensure protection of patient confidentiality and safety. At each meeting, the DSMB will make recommendations as to whether the studies should continue or if changes to the protocol are necessary for continuation. The DSMB will also review periodic safety reports from SO, as needed. This trial has been registered with clinicaltrials.gov.

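### Section 6.3 calls adverse event tracking infeasible yet expects to hear of every event; EHR-recorded harms could be counted by arm, but their extraction is not specified

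*Combined protocol and SAP*

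**What the plan says.** Section 6.3 makes three statements that bear on each other.

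- On feasibility, it says that "prospectively tracking adverse events is infeasible", and of active monitoring it adds: "which if done would require patient contact and detailed patient-level chart-reviews".
- On completeness, having named voluntary reports from physicians and contact with practice and divisional leadership as the only channels, it says: "we anticipate that the study team will be informed of any AEs or SAEs that do occur".
- On expected risk, it says that "any adverse events as part of this study are expected to be similar, or lower, than those anticipated in routine hypertension care".

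The same section defines an adverse event broadly, related or not, and includes abnormal laboratory and examination findings. Its serious events include death and hospitalisation.

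Section 3.7 says that patients' "medical history, disease control, medication use and health care utilization will be obtained from EHR data", and that "The various tables within the Clarity database are refreshed on a daily, weekly or monthly basis". Section 6.2 takes the last recorded blood pressure within 6 months after the targeted visit, in every arm. Section 7.3 contains no analysis of harms by arm.

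**The concern.** The trial sets out to increase antihypertensive prescribing. Section 8.1 acknowledges hypotension, bradycardia and allergic reactions as possible consequences, and Section 8.2 asks for a waiver of patient consent partly on the ground of minimal risk. The randomised control arm is the natural benchmark for ordinary care, but nothing in the plan compares harms with it.

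The Safety Officer and the DSMB would receive only what somebody chose to report. If few or no reports arrive, the Section 6.3 expectation of being informed invites them to read silence as absence of harm. The reporting channel cannot support that reading.

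**Working it through.** **Does the infeasibility reason follow?** Set the sections side by side.

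- *What counts as an event (6.3).* Death, hospitalisation and abnormal laboratory findings can appear in a health record without anyone speaking to a patient. Ungraded symptoms often cannot.
- *What the study can reach (3.7).* Utilisation, medication and disease-control data, from tables refreshed at least monthly.
- *What it already follows (6.2).* Targeted patients in all three arms, to 6 months, for one blood pressure.
- *What chart access it already uses (5.2).* A pharmacist reviews each listed arm 1 patient's chart before the visit. This shows access; it gives no information on later harms.
- *What is actually specified.* Utilisation is a visit count over the 12 months before baseline (6.1). Creatinine is listed as baseline data and as a model variable (6.1, 6.2) with no follow-up time. The only post-visit clinical measurement is the single last blood pressure, with about 20% expected missing (6.2).

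So the reason fails for events recorded in the EHR and holds for those that are not. The source is accessible, but the extraction window would have to be extended.

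**What can volunteered reports show?** The documents give no event rate and no capture rate, so there is no figure of the plan's to reproduce. Arm size comes from Section 7.2: 15 physicians × 12 patients = 180 per arm. The event rates and capture fractions below are assumptions, and patients are treated as independent.

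Expected reports per arm = 180 × rate × capture. P(no reports) = (1 − rate × capture)^180.

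| Assumed true rate | Capture | Expected reports | P(no reports) |
|---|---|---|---|
| 5% | 10% | 0.9 | 41% |
| 5% | 25% | 2.25 | 10% |
| 5% | 100% | 9.0 | 0.01% |

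Suppose the true rate doubles, from 5% in control to 10% under intervention. From the two binomial distributions, the intervention arm shows no more reports than control with probability 41% at 10% capture and 25% at 25% capture, against 4% with complete capture.

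Unequal capture distorts the same doubling in either direction:

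- 10% in intervention, 20% in control: (10% × 0.10) / (5% × 0.20) = 1.0% / 1.0% = a ratio of 1.0.
- 25% in intervention, 10% in control: (10% × 0.25) / (5% × 0.10) = 2.5% / 0.5% = a ratio of 5.0.

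**What would complete EHR capture give?** The design effect with the Section 7.2 ICC of 0.05 is 1 + (12 − 1) × 0.05 = 1.55, so the effective size is 180 / 1.55 = 116.1 per arm. That ICC is stated for intensification; using it for harms is an assumption. The 95% half-width for a difference between two arms at equal rate p is 1.96 × √(2p(1 − p)/n).

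| Assumed rate | n = 180 | n = 116.1 |
|---|---|---|
| 2% | ±2.9 points | ±3.6 points |
| 5% | ±4.5 points | ±5.6 points |
| 10% | ±6.2 points | ±7.7 points |

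Power to detect a doubling from 5% to 10% (two-sided 5%) is 44% without clustering and 30% with it.

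**The case against.** The best defence is that the Section 6.3 definition covers any untoward sign, symptom or disease, graded for severity and expectedness. Coded data cannot supply that, so full tracking really would need contact or chart review. This stands, and it is why the infeasibility statement should be narrowed and not struck out. It is also true that this is a physician-facing pilot with an independent Safety Officer and a DSMB, and that even complete capture would be imprecise.

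Five stronger readings are tempting, and the documents do not support them.

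- *That the harm data are already being pulled.* They are not: no post-visit admissions, emergency visits, coded events or follow-up creatinine are specified. One last blood pressure could miss transient hypotension.
- *That the plan relies on volunteered reports to prove risk is no higher.* It offers that as a prior expectation, argued from physician discretion, a cited trial and the type of patient. The waiver request in Section 8.2 cites minimal risk, no patient interaction and impracticability.
- *That reporting differs by arm.* It may: arm 1 physicians get a message per patient, arm 2 a weekly list, and control physicians nothing. But Section 8.2 gives all invited physicians the study contacts, and the leadership channels are not arm-specific. Differential reporting is plausible, not shown.
- *That oversight comes too late.* Section 8.4 says "Meetings of the DSMB will be held regularly (e.g., every six to nine months", which is longer than much of the intervention period. But the interval is an example, and meetings can be called by the funder or the chair. Section 6.3 sends deaths within 24 hours, unexpected serious events within 48 hours and the rest quarterly. The weakness is what reaches this channel, not how quickly it moves on.
- *That zero reports would bound the risk.* For 0 of 180 the one-sided 95% upper limit is 1 − 0.05^(1/180) = 1.65%. That describes one arm, needs complete capture, ignores clustering and says nothing about a difference from control.

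**Conclusion.** The concern holds in a limited form. For EHR-recorded events the infeasibility reason conflicts with the plan's own definitions, data source and 6-month follow-up. The expectation of being informed of events as they occur is unsupported for a volunteer channel covering about 45 × 12 = 540 patients. No comparison of harms by arm is planned.

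The size depends on assumptions, because the documents give neither event rates nor capture rates. At 10% capture and a 5% true rate, an arm would produce no reports about four times in ten. This affects the safety information, not the primary efficacy analysis. The change is worth making, but the resulting counts should not be presented as a test of the expectation that risk is no higher than in usual care.

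**What to change.** 1. In Section 6.3, limit the infeasibility statement to symptoms and other events that the EHR does not record.
2. In Section 6.3, delete the expectation that the team will be informed of the events that occur, and say that volunteered reports are of unknown completeness.
3. In Sections 3.7 and 6.2, extend the existing EHR query, identically for targeted patients in all three arms over the 6-month follow-up. Cover deaths, hospitalisations, emergency visits, coded hypotension, syncope or bradycardia, and recorded low blood pressure and creatinine change. The study team should state the definitions before extraction.
4. In Section 7.3, add a descriptive table of counts by arm with cluster-adjusted confidence intervals, and say that it is not a demonstration of equal risk.
5. In Sections 6.3 and 8.4, send the table to the Safety Officer once during and once after the intervention period.

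The cost is a modest further data pull and one table, with no patient contact or chart review. The added fields must stay within the minimum-necessary terms of the waiver. Three limits should be stated beside the table. Coded events are non-specific and must be read against control. Blood pressure and creatinine are seen only when measured, and treatment intensification may itself change how often that happens. At this sample size the intervals will be wide.

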7.1 Statistical Hypotheses

The null hypothesis is that rates of hypertension treatment intensification will be equal in each of the intervention groups when compared to control.

7.2 Sample size determination

Because we are selecting specifically for patients with clinical inertia, we expect the control arm rate of medication intensification at the target office visit to be no more than 15%. Assuming an ICC of 0.05, a type I error rate of 5%, and 12 patients per physician over the study period, a sample size of 45 physicians (i.e. 15 per arm) will provide more than 80% power to detect a 15% difference in treatment intensification between each intervention group and control. If the control arm intensification rate is higher than anticipated, we will still be sufficiently powered for reasonable effect sizes (i.e. if the rate of the primary outcome in the control arm was 0.2%, we will be able to detect an effect size of 17%). These data are intended to provide pilot data for larger evaluations, and any positive signal from this pilot trial will help inform next steps. If we have more eligible and

consented physicians than originally anticipated, we will adjust our allocation scheme so that additional physicians are allocated to the control arm to maximize power.

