Physicians will be informed about the study and agree to participate using an online consent process through RedCap, and then will be asked to complete a set of behavioral surveys administered through RedCap. PCPs will then be randomized to one of the two intervention arms or control arm. To minimize imbalance between treatment groups, we will use block stratified randomization. Based on the number of sessions per week, providers will be determined to have a small (1-2 sessions), medium (3-4 sessions), or large (5 or more sessions) panel. Within each stratum, we will array physicians into blocks of 3 (note: could also be multiples of 3). All possible balanced combinations of assignment within the block will be allowed in each stratum. Ultimately, within each block and each stratum, physicians will have an equal probability of being assigned to one of the 3 arms.

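### The claim of more than 80% power in section 7.2 is slightly too high with equal clusters, and it makes no allowance for unequal numbers of patients per physician

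*Combined protocol and SAP*

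**What the plan says.** Section 7.2 gives all the planning inputs. For the control arm, "we expect the control arm rate of medication intensification at the target office visit to be no more than 15" percent. The clustering input is "Assuming an ICC of 0.05", and the significance level is "a type I error rate of 5" percent, with sidedness not stated. Cluster size enters as a single figure, with no standard deviation, range or CV: "12 patients per physician over the study period, a sample size of 45 physicians (i.e. 15 per arm) will provide more than 80% power". The claim is for a 15-point difference, for each intervention arm against control.

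Other parts of the document bear on how many patients each physician will contribute:

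- Section 3.2.1 (repeated in 5.3) stratifies randomisation by workload: "providers will be determined to have a small (1-2 sessions), medium (3-4 sessions), or large (5 or more sessions) panel".
- The summary of changes gives the reason for that stratification and describes sessions per week as proportional to panel size.
- Sections 3.2.1 and 4.1 set the minimum at 2 qualifying patients per physician. Section 4.2 sets a minimum panel of 100 and at least one session a week.
- Section 7.3.1 analyses the primary outcome with a logit-link GEE clustered by provider.

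**The concern.** With a positive ICC and a fixed mean cluster size, spread in cluster size lowers the effective sample size. The plan's strata run from 1-2 sessions a week to 5 or more, and the eligibility rule allows clusters far below 12, so some spread is to be expected. A figure computed for equal clusters is then an upper bound for these inputs. It would need slack to support a claim of more than 80%, and the question is whether it has any.

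What is at stake is how the result is read. This is a pilot meant to inform larger evaluations. A non-significant comparison will be judged against the stated power, and the same calculation may be carried into the next trial.

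**Working it through.** **Inputs from section 7.2.** 15% versus 30%; 15 physicians per arm; mean 12 patients, so 15 × 12 = 180 per arm; ICC 0.05; alpha 5%.

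**Sidedness (assumed two-sided).** Section 7.2 also says that "if the rate of the primary outcome in the control arm was 0.2%, we will be able to detect an effect size of 17" percent. I read the 0.2% there as a rate of 0.2, that is 20%. With equal clusters and a 20% control rate, the difference detectable with 80% power is 16.3-16.5 points two-sided and 14.5 points one-sided (pooled variance). The stated 17 fits two-sided.

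**Step 1: the plan's own figure, equal clusters.**

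- Design effect = 1 + (12 − 1) × 0.05 = 1.55. Effective n per arm = 180/1.55 = 116.1.
- Variance sum = 0.15 × 0.85 + 0.30 × 0.70 = 0.1275 + 0.21 = 0.3375.
- Unpooled: Φ(0.15/√(0.3375/116.1) − 1.96) = Φ(2.782 − 1.96) = 79.5%.
- Pooled (null variance 2 × 0.225 × 0.775 = 0.34875): Φ((0.15 − 1.96 × √(0.34875/116.1))/√(0.3375/116.1)) = 78.5%.

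The arcsine method gives 79.2%. So 80% is reproduced to within 2 points, but none of these two-sided calculations exceeds it. The pooled formula needs an effective n of about 120.5, that is a design effect of at most 180/120.5 = 1.49.

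**Step 2: unequal clusters, mean held at 12.** Two standard forms:

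- Independence weighting: design effect = 1 + ((1 + CV²) × 12 − 1) × 0.05.
- Exchangeable weighting: effective n = Σ mᵢ/(1 + (mᵢ − 1) × 0.05), where mᵢ is the number of patients of physician i.

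The CV is not in the documents. My assumption is one third of physicians in each stratum and patients proportional to sessions, with 1.5, 3.5 and S sessions a week, where S (the top stratum) is varied from 5 to 8.

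Worked case, S = 6: sizes 4.9, 11.5 and 19.6; CV 0.50.

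- Independence: 1 + (1.25 × 12 − 1) × 0.05 = 1.70; effective n = 180/1.70 = 105.9; unpooled power = Φ(0.15/√(0.3375/105.9) − 1.96) = 75.7%; pooled 74.7%.
- Exchangeable: 5 × (4.9/1.195 + 11.5/1.525 + 19.6/1.93) = 109.0; power 76.9% unpooled, 75.9% pooled.

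Each cell below gives pooled then unpooled power, 15% versus 30%:

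| Scenario | CV | Independence | Exchangeable |
|---|---|---|---|
| Equal | 0 | 78.5%, 79.5% | same |
| Mild spread | 0.2 | 77.9%, 78.9% | 78.1%, 79.1% |
| S = 5 | 0.43 | 75.7%, 76.7% | 76.5%, 77.5% |
| S = 6 | 0.50 | 74.7%, 75.7% | 75.9%, 76.9% |
| S = 8 | 0.63 | 72.6%, 73.6% | 74.6%, 75.6% |

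The strata-based scenarios span 72.6% to 77.5%, a loss of about 2 to 6 points from the equal-cluster figure. At CV 0.2 the loss is 0.4-0.6 points.

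**Step 3: detectable difference at 80% power, 15% control rate.** Equal clusters: 15.1-15.3 points. CV 0.5: 15.6-16.1 points.

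**Step 4: lower control rate.** At 10% versus 25%, power is 85.7-86.6% with equal clusters and 80.5-85.0% across S = 5 to 8.

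**Step 5: simulation of an arm-only logit GEE (beta-binomial, ICC 0.05).** With the uncorrected sandwich error, power is 80.2% for equal clusters and 77.6% for sizes 5/11/20, but the type I error is about 7%. With a small-sample-corrected error and t on 28 df, type I error is about 5% and power is 75.5% and 72.5%.

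**The case against.** The strongest reply is that the effect is small and its size is assumed. The plan gives neither the share of physicians in each stratum nor the spread of targeted patients. What counts is patients with clinical inertia who have a visit in the window, not panel size. This stands: the direction of the effect follows from the formula, but the 2-6 points rest on my assumptions.

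Second, 15% is stated as an upper limit, and at 10% versus 25% the claim survives. That also stands, and it limits the point to the planning value. But section 7.2 builds its claim on 15% and itself considers a higher control rate, at which power for 15 points would be lower.

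Third, the ICC matters more. At CV 0.5 with independence weighting, unpooled power is 82.8% at ICC 0.03 and 69.2% at ICC 0.07. True, but that does not rescue the figure at the stated ICC. A one-sided 5% test would keep power at 82% or more in these scenarios, but the companion figure of 17 points fits a two-sided test.

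Fourth, an uncorrected GEE reaches 80.2% with equal clusters in the simulation, and 80-82% when adjusted for stratum. It does so partly through an inflated type I error, and it still falls to about 78% with sizes 5/11/20.

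Three stronger readings are tempting, and the documents do not support them:

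- A reader might infer that any spread takes power clearly below 80%. A CV of 0.2 costs under 1 point.
- A reader might infer that unequal clusters alone cause the shortfall. Equal clusters already miss by about a point, and section 7.2 does not say that every physician has exactly 12 patients; it only omits a variation term.
- A reader might apply a CV of 0.8 or 1.0 and quote much lower power. The strata, under the assumptions above, give only about 0.4-0.6.

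**Conclusion.** At its own planning inputs (15% versus 30%, ICC 0.05, 15 physicians per arm, mean 12 patients, two-sided 5%), the plan does not deliver more than 80% power. Equal clusters give about 78.5-79.5%, a rounding-level overstatement. Variation of the kind the strata suggest takes power to about 73-78%. The second range depends on equal thirds and on patients proportional to sessions, neither of which the documents state. The shortfall is modest and does not undermine the design of a pilot. It is worth correcting because the power is a headline planning figure, will frame any null result, and is cheap to restate.

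**What to change.** In section 7.2:

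1. Replace the equal-cluster calculation with design effect 1 + ((1 + CV²) × 12 − 1) × 0.05, or the exchangeable equivalent, and state which weighting and sidedness are used.
2. Take a provisional mean and CV of qualifying patients per physician from the EHR eligibility extract, before randomisation. Say that this is a proxy, because the extract looks back at blood pressure history while the analysis counts targeted visits in the intervention period.
3. Replace the claim of more than 80% with the resulting power over a stated CV range. As an illustration for a 15% control rate: about 79% for a 15-point difference if clusters are equal, about 75-77% at CV 0.5, and 80% power for a difference of about 16 points.

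The cost is one recalculation and a revised sentence or two. No physicians need be added and the design does not change. The downside is that the stated power becomes slightly less favourable.
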